8.2.3 Ketone Ester Drink Storage & Distribution

The ketone ester drinks are stored at room temperature. Stocks of the drink will be kept in a storage area in the Advanced Imaging Centre. Participants will be given a 2 week supply of the drink at their first study visit.

8.2.4 Potential risks and hazards

MR is safe, with no known risks. The contrast medication is safe, but rarely reactions may occur. The department is equipped to cope with allergic reactions if they happen. Dobutamine can cause breathlessness and chest discomfort, subsiding within minutes of the medication being stopped. Oral Ketone supplements are safe and should not cause any significant side effects at the recommended doses. Mild nausea might be experienced by the participants, they will therefore be fully informed of this potential side effect. Participants will be provided 24hour access to investigators and will be asked to contact the study team directly should they experience this side effect. The investigators, who are medically qualified NHS doctors, will organise an urgent review (within 24 hours) and assess the participants with physical examination. Participants will be asked to hold the next dose of ketone ester until they have been reviewed. Patients will be monitored and cardiology team will be present during the CMR studies. The oral ketones have been safely administered to patients with diabetes. While oral supplementation was not assessed in heart failure patients previously, another study assessed higher doses of ketone infusion in heart failure patients and demonstrated its safety³⁹.

Ketones are naturally produced energy fuels by the liver. Ketones have been safely delivered per orally with no complications in healthy volunteers and intravenously even in patients with severe heart failure^{39,}
⁴⁹. Ketone will be delivered via per oral administration for a course of 2 weeks in the form of a ketone ester drink three times daily. No side effects are expected at this dose and duration in the patients or controls.

During the scan acquisitions, participants will also hold a buzzer in their dominant hand and will be able to use the buzzer to attract attention immediately for any reason while in the scanner. The study investigators are all medically qualified stuff (consultant cardiologists or cardiology trainees and nurses) who will be present at all times during the research visits, which will be conducted in an hospital environment.

The exact nature of the study and the risks involved in taking part will be explained to participants. They will have the option to leave the study at any point, and will be given the contact details of study investigators to share any concerns they may have. The study will be conducted in full conformance with Good Clinical Practice, and NHS indemnity will operate.

Document: Research Protocol	
Short Title: KICK-Energy	Version 2.0
Chief Investigator: [name]	Date 09 Mar 2023
IRAS Project ID: 308642	Page 18 of 32

8.3 Image Analysis

All imaging will be analysed blinded to patient details. Images will be allocated a computer-generated random number, the key to which will not be accessible to staff involved in the analysis until all analyses have been completed and the database has been locked.

³¹P-MR Spectroscopy: ³¹P-MRS post processing analysis will be performed using Matlab version R2012a (Mathworks, Natick, Massachusetts) as previously described⁵⁰.

Cardiac Volumes and Function: CMR data will be assessed quantitatively using commercially available software (CVI42, Circle Cardiovascular Imaging Inc, Calgary, Canada). Epicardial and endocardial borders will be traced offline on the LV cine stack at end-diastole and end-systole to calculate end-diastolic, end-systolic LV volumes, stroke volume, ejection fraction, and LV mass, as previously described⁵¹. Feature tracking analysis will be performed using cvi42. The peak systolic circumferential strain, global longitudinal strain and diastolic strain rate data will be measured.

Myocardial Perfusion: The endo- and epicardial borders for the basal, mid-ventricular and apical short-axis images will be manually delineated both at rest and stress. Similar to oxygenation analysis, the myocardium will be divided into equiangular segments on the basis of the American Heart Association segmentation model. Myocardial perfusion (MP) in ml/min/g will be assessed globally (average myocardial perfusion for 16 segments). MP reserve will also be calculated, defined as the ratio between MP at stress over rest. In-line automatic reconstruction and post-processing of the perfusion data will be implemented within the Gadgetron software framework⁴⁵. Images will be motion corrected and then corrected for surface coil intensity variation based on the proton density weighted images. Signal intensity data will be converted to Gadolinium concentration based on automatically generated look-up tables. AIF data will be extracted from the low-resolution Gadolinium concentration images using automated segmentation of the LV cavity. Myocardial blood flow will be calculated on a pixel-wise basis in the high-resolution images by blood tissue exchange model constrained deconvolution incorporating estimation of the delay time between bolus arrival in the LV cavity and the tissue of interest.

Late gadolinium Imaging: For LGE analysis, areas of contrast enhancement will be visually scored as absent or present by consensus of 2 experienced operators. LGE will be considered present only if myocardial enhancement was confirmed on both short-axis and matching long-axis locations.

8.4 Discontinuation/Withdrawal of Participants

Each participant has the right to withdraw from the trial at any time. In addition, the Investigator may discontinue a participant from the trial at any time if the Investigator considers it necessary for any reason including:

- Pregnancy
- Ineligibility (either arising during the trial or retrospectively having been overlooked at screening)
- Significant protocol deviation
- An adverse event to gadolinium contrast or dobutamine injection during the baseline visit
- Withdrawal of Consent

Document: Research Protocol	
Short Title: KICK-Energy	Version 2.0
Chief Investigator: [name]	Date 09 Mar 2023
IRAS Project ID: 308642	Page 19 of 32

Where patients wish to withdraw from the study, clarification of the extent of withdrawal will be sought and documented in the CRF. Patients who withdraw from the study will be replaced.

If the participant is withdrawn due to an adverse event, the Investigator will arrange for follow-up visits or telephone calls until the adverse event has resolved or stabilised.

8.5 Definition of End of Study

The end of trial is the date of the last visit of the last participant.

9 Safety Reporting

9.1 Definitions

Adverse Event (AE)

An AE or adverse event is:

Any untoward medical occurrence in a patient or clinical investigation participants, which does not necessarily have a causal relationship with this treatment.

An AE can therefore be any unfavourable and unintended sign (including an abnormal laboratory finding), symptom or disease temporally associated with the study, whether or not considered related to the study.

Serious Adverse Event

A serious adverse event is any untoward medical occurrence that:

- Results in death,
- Is life-threatening,
- Requires inpatient hospitalisation or prolongation of existing hospitalisation,
- Results in persistent or significant disability/incapacity,
- Is a congenital anomaly/birth defect, or
- Other important medical events*

NOTE: The term "life-threatening" in the definition of "serious" refers to an event in which the participant was at risk of death at the time of the event; it does not refer to an event which hypothetically might have caused death if it were more severe.

*Other events that may not result in death, are not life threatening, or do not require hospitalisation, may be considered a serious adverse event when, based upon appropriate medical judgement, the event may jeopardise the patient and may require medical or surgical intervention to prevent one of the outcomes listed above.

Document: Research Protocol	
Short Title: KICK-Energy	Version 2.0
Chief Investigator: [name]	Date 09 Mar 2023
IRAS Project ID: 308642	Page 20 of 32

An SAE occurring to a research participant, which in the opinion of the Chief Investigator is Related and Unexpected will be reported to the main Research Ethics Committee (REC). Related and Unexpected SAEs are defined as: i) Related: it resulted from administration of any research procedures; and ii) Unexpected: the type of event is not listed in the protocol as an expected occurrence.

9.2 Causality

The assignment of the causality should be made by the investigator responsible for the care of the participant using the definitions in the table below. All adverse events judged as having a reasonable causal relationship to study procedures (i.e. definitely, probably or possibly related) are considered to be adverse events. In the case of discrepant views on causality between the investigator and others, all parties will discuss the case. In the event that no agreement is made, the REC and other bodies will be informed of both points of view.

Relationship	Description
Unrelated	There is no evidence of any causal relationship
Unlikely	There is little evidence to suggest there is a causal relationship (e.g. the event did not occur within a reasonable time after conducting study procedures). There is another reasonable explanation for the event (e.g. the participant's clinical condition, other concomitant treatment).
Possible	There is some evidence to suggest a causal relationship (e.g. because the event occurs within a reasonable time after conducting study procedures). However, the influence of other factors may have contributed to the event (e.g. the participant's clinical condition, other concomitant treatments).
Probable	There is evidence to suggest a causal relationship and the influence of other factors is unlikely.
Definitely	There is clear evidence to suggest a causal relationship and other possible contributing factors can be ruled out.
Not assessable	There is insufficient or incomplete evidence to make a clinical judgement of the causal relationship.

9.3 Severity

Severity of all AEs will be graded on a three-point scale of intensity (mild, moderate or severe):

Mild	Discomfort is noticed, but there is no disruption of normal daily activities.

Document: Research Protocol		
Short Title: KICK-Energy Version 2.0		
Chief Investigator: [name]	Date 09 Mar 2023	
IRAS Project ID: 308642	Page 21 of 32	

Moderate	Discomfort is sufficient to reduce or affect normal daily activities.	
Severe	Discomfort is incapacitating, with inability to work or to perform normal daily activities.	

Note: An AE may be severe but not serious. The term "severe" is often used to describe the intensity (severity) of a specific event (as in mild, moderate, or severe myocardial infarction); the event itself, however, may be of relatively minor medical significance (such as severe headache). This is not the same as "serious," which is based on patient/event outcome or action criteria usually associated with events that pose a threat to a participant's life or functioning. Seriousness (not severity) serves as a guide for defining regulatory reporting obligations.

9.4 Expected AEs & SAEs- Not Reportable

Due to the nature of T2D and heart failure, participants with this condition may experience adverse events during the course of their disease.

9.5 Expected AEs & SAEs- Reportable

The following events are expected within the study population and will be reported by the clinical research team using standardised Case Report Forms (CRFs).

T2D Patients:

- Hypoglycaemia
- Routine treatment or monitoring of the studied indication (T2D) not associated with any deterioration in condition

Heart Failure Patients:

- Exertional breathlessness (these are controlled heart failure patients under the care of heart failure team, therefore they are expected to be well managed by the clinical team)
- Routine treatment or monitoring of the studied indication (HF) not associated with any deterioration in condition

These events are expected within the study population and will not be subject to expedited reporting to the main REC. All non-serious or expected adverse events will be recorded on the study CRF. In keeping with HRA guidelines, reports of Serious Adverse Events (SAEs) that are related and unexpected will be submitted to the REC using the HRA Non-CTIMP safety report to REC form within 15 days of the chief investigator becoming aware of the event and will be reported to the sponsor within 1 working day of the research team becoming aware of the event.

Events will be followed up until the event has resolved or a final outcome has been reached.

Document: Research Protocol		
Short Title: KICK-Energy Version 2.0		
Chief Investigator: [name]	Date 09 Mar 2023	
IRAS Project ID: 308642	Page 22 of 32	

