Exogenous ketone ester: The ketone bodies, D-beta-hydro- xybutyrate (βHB) and acetoacetate, are not readily available in the human diet, but are produced in the liver from free fatty acids in response to low blood glucose and insulin levels, as an alternative to glucose as an energy supply for the brain. Until recently, blood ketones could only be raised over several days by fasting or by strictly following low-carb, high-fat diets. Similar blood βHB concentrations can now be attained within 30 min by drinking the ketone monoester, (R)-3-hydroxybutyl (R)-3-hydroxybutyrate, which introduces a new metabolic state, termed exogenous nutritional ketosis. Interventions that induce ketosis simultaneously lower blood glucose, as a result a recent study has assessed safety, tolerability, and effects of an exogenous ketone ester supplementation on glycaemic control in 21 patients with T2D ³⁷. The participants consumed 25 ml of ketone ester product 3 times daily for 4 weeks. This study assessed serum electrolytes, acid-base status, and beta hydroxybutyrate concentrations weekly and cardiovascular risk markers were measured before and after the intervention. The investigators have shown that exogenous ketosis using a ketone ester product was capable of inducing fasting-like elevations in serum β-hydroxybutyrate without the need for caloric or carbohydrate restriction. Importantly constant ketone ester consumption over 1 month was safe, well tolerated, and improved glycaemic control in patients with T2D. Safety of the same ketone ester product has also been shown in healthy volunteers³⁸. The only side effect detected in both studies was mild nausea.

While oral supplementation was not assessed in heart failure patients previously, another study assessed higher doses of ketone infusion in heart failure patients and demonstrated its safety³⁹

³¹Phosphorus Magnetic Resonance Spectroscopy and Myocardial Energetics Magnetic resonance spectroscopy (MRS) is the only noninvasive, non-radiation exposure technique for the investigation of

Document: Research Protocol	
Short Title: KICK-Energy	Version 2.0
Chief Investigator: [name]	Date 09 Mar 2023
IRAS Project ID: 308642	Page 9 of 32

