8.2 Study Assessments

8.2.1 Blood Tests and Urine Pregnancy Test

Blood will be taken via venipuncture at visit 1 and visit 2. At Visits 1 and 2, the levels of plasma lipids, insulin, beta-hydroxybutyrate, acetoacetate, and glucose will be measured. At Visit 1, U&Es and HbA1c will also be measured. These blood tests are purely for research purposes. No additional interventions should be needed due to the results and participants will adhere to their usual treatment plans (if applicable).

Participants will be administered a urine pregnancy test at their first study visit (if applicable).

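### Sections 9.1 and 9.5 together class a serious hypoglycaemia (T2D) or exertional breathlessness (heart failure) caused by the ketone drink as expected, so no expedited report is required

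*Protocol*

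**What the plan says.** Four parts of the protocol bear on this.

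- **The list.** The section headed "9.5 Expected AEs & SAEs- Reportable" names hypoglycaemia for T2D patients. For heart failure patients it names "Exertional breathlessness (these are controlled heart failure patients under the care of heart failure team", with a remark that they should be well managed clinically. Each group also has a bullet for routine care, restricted to care without deterioration. The hypoglycaemia and breathlessness bullets carry no such restriction. The section then states: "These events are expected within the study population and will not be subject to expedited reporting to the main REC".
- **The definition.** Section 9.1 calls an SAE related if it resulted from a research procedure, and unexpected if "the type of event is not listed in the protocol as an expected occurrence".
- **The routes.** Sections 9.5 and 9.7 contain the same sentence. SAEs that are related and unexpected go to the REC within 15 days of the chief investigator becoming aware, and to the sponsor within 1 working day of the research team becoming aware. Expected events are recorded on the CRF. No other deadline for telling the sponsor of an SAE is written.
- **What is said of the drink.** Section 4.1 says "Interventions that induce ketosis simultaneously lower blood glucose". Section 8.2.4 allows for mild nausea, then says that no side effects are expected at this dose and duration. It also says of the oral product: "While oral supplementation was not assessed in heart failure patients previously".

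**The concern.** The 9.5 list describes what the diseases may produce. Section 9.1 then uses it to decide what is unexpected about the study. An event can be common in T2D and still, in a given participant, be caused by the drink. A rule based on type alone cannot tell the two apart.

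This matters most for hypoglycaemia, because the protocol itself gives a mechanism by which the drink could cause it. Under section 7, T2D participants may be on any kind of glucose-lowering therapy, and under section 8.1 they continue their prescribed medication. The home finger-prick test in section 8.1 measures ketones, not glucose.

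At stake is how soon the REC and the sponsor learn of a serious event that the investigator attributes to the intervention. The efficacy analysis is not affected.

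**Working it through.** No arithmetic settles this. The check takes serious events judged related to the drink and follows each through 9.1, 9.5 and 9.7. It assumes that the drink counts as a research procedure under 9.1, and that the 9.5 list applies group by group.

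| Event (serious, judged related to the drink) | Listed in 9.5? | Unexpected under 9.1? | Report required |
|---|---|---|---|
| T2D patient, hypoglycaemia with hospital admission | Yes | No | CRF entry only |
| Heart failure patient, exertional breathlessness meeting an SAE criterion | Yes | No | CRF entry only |
| Heart failure patient, breathlessness at rest or decompensation | No | Yes | REC 15 days, sponsor 1 working day |
| Healthy volunteer, hypoglycaemia | Not for this group | Yes | REC 15 days, sponsor 1 working day |
| Heart failure patient who also has T2D, hypoglycaemia | Unclear | Unclear | Unclear |

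Step by step for the first row:

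1. Hospital admission meets the 9.1 definition of an SAE.
2. The investigator judges it caused by the drink, so it is related.
3. Hypoglycaemia is a listed type for T2D, so it is not unexpected.
4. The condition for expedited reporting is related **and** unexpected. It fails on the second part.
5. What remains is the CRF entry and follow-up.

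The first and fourth rows show the oddity. The same serious, drink-related event is expedited in a healthy volunteer but not in a T2D patient, who may also be taking glucose-lowering drugs.

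Three comparisons within the protocol point the same way.

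- The note in 9.3 says that seriousness guides reporting obligations. Under 9.1 and 9.5 a listed type overrides seriousness.
- Section 4.1 expects a glucose-lowering effect, while 8.2.4 expects no side effects from the drink. Section 9.5 then treats hypoglycaemia as background illness.
- Section 9.4, on expected events that are not reportable, says only that these patients may have adverse events from their disease. It names no types and sets no limit, so it does not help to separate disease from drink.

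Other routes were checked for a prompt alternative. Section 9.6 records every AE with its relatedness. Section 9.2 takes an unresolved disagreement on causality to the REC. The steering committee in 10.4 meets twice a year, and safety review is not in its listed remit. The progress report in 13.4 is annual or on request. None of these gives prompt notice of a case on whose cause everyone agrees.

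On size: the two listed groups are 30 + 30 = 60 of the planned 90 participants. That counts people to whom the list applies, not events misrouted.

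**The case against.** The strongest defence is that expediting only related and unexpected SAEs is the rule the protocol attributes to HRA guidelines, and that some list of expected disease events is ordinary. That stands, and the point leaves the rule alone. The weakness is the unrestricted list that feeds it.

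It can also be said that the evidence cited in the protocol is reassuring. In section 4.1 the two oral studies found only mild nausea, and a study of higher-dose infusion in heart failure is described as showing safety. No section links the drink to breathlessness. This lowers the likely number of cases, and it makes the argument weaker for breathlessness than for hypoglycaemia. It does not change where a case would go.

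Three stronger readings may tempt a reader, and the protocol does not support them.

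- *Worsening heart failure is classed as expected.* It is not on the 9.5 list. Only exertional breathlessness is, and the neighbouring bullet excludes deterioration. The vagueness of 9.4 makes this less clear than it should be, but it lists no such event.
- *The sponsor would not be told at all.* The explicit exclusion in 9.5 names the main REC. For the sponsor it follows only from the absence of any other SAE deadline. Nothing forbids notification, and 9.6 has the sponsor able to judge relatedness. The text supports only that no expedited report is required.
- *Safety monitoring is deficient because urea and electrolytes are scheduled only at Visit 1.* That is a separate matter. It contradicts nothing in the protocol, and tolerability is not a stated objective.

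**Conclusion.** The point holds as a gap in the reporting rules. A related SAE that is hypoglycaemia in a T2D patient, or exertional breathlessness in a heart failure patient, requires neither the 15-day REC report nor the 1-working-day sponsor report. For the REC this is explicit; for the sponsor it is the plain consequence of the only deadline written.

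Its size is two event types in two of the three groups. The expected number of such events cannot be derived from the protocol, and a confidence limit for zero events in 30 patients would not measure the defect, since it would be the same under any reporting rule.

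The conclusion assumes that 9.1 and 9.5 are applied literally and that the drink counts as a research procedure. If the drink did not count, the event would also fail the first condition, and again no expedited report would be required. The change is worth making because it is cheap and protects participants, not because any planned analysis depends on it.

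**What to change.** - **9.5:** limit the expected list to non-serious events attributable to the underlying disease. State that any listed event that meets an SAE criterion and is judged related to the drink or to study procedures is treated as unexpected and follows 9.7 to the REC and the sponsor.
- **9.1:** amend the definition of unexpected so that it no longer rests on event type alone, and say that the drink counts when relatedness is judged.
- **9.4:** say which events it covers and that it does not override 9.5 or 9.7. In 9.5, say how hypoglycaemia is handled in heart failure participants who also have T2D.
- **4.1 and 8.2.4:** reconcile the stated glucose-lowering effect with the statement that no side effects are expected, so that expectedness is judged against the intervention as well as the disease.

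The cost is a protocol amendment to wording and a few additional expedited reports. No visit, sample or analysis changes.
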